Within 24 hours of admission to the inpatient floor, study subjects will be approached by a member of the research team, and asked for informed consent. Patients that consent to participate and meet our inclusion criteria will be ordered the appropriate study drug by the floor pharmacist, per the Yale Investigative Drug Service's randomization to either the treatment or the placebo arm. Each subject will be ordered a capsule containing either placebo (cellulose microcrystalline) or 5 mg melatonin each evening at 9 p.m. The study drug can be given as early as 7pm on the day of admission, if necessary, to allow treatment to begin within 24 hours of admission to the floor.. The capsules will be prepared and administered by the Yale-New haven Hospital Investigational Drug Service. The capsules will be administered nightly until discharge or a maximum of 2 weeks if the hospitalization is prolonged. The capsule must be swallowed whole and not opened.

Subjects will be assessed twice daily, once in the- a.m. and again in the p.m by the floor nurses for evidence of delirium using the Short CAM (Confusion Assessment Method), which is a validated clinical tool for identifying delirium, and the current standard of practice tool for the diagnosis of delirium. This evaluation should take maximally 5 to 10 minutes to complete.

While it is considered standard of care for nurses to administer the Short CAM once daily at Yale-New Haven Hospital, the twice daily Short CAM is standard of care at the University of Connecticut Hospital but not currently at the Yale-New Haven Health System with the exception of Verdi 4 West where the CAM is administered twice a day for all patients.

The primary endpoint will be the occurrence of delirium as defined by the Short CAM by the time of discharge or prior to hospital day 15, whichever occurs first. The study drug will be continued until the primary end point of delirium is reached, discharge or hospital day 15.

The maximum period of study drug administration will be 14 days. If the patient's length of stay exceeds 14 days the patient's participation in the study will end and the subject will be recorded as having completed the study without delirium. If the primary end point of delirium is reached, the subject will have completed the study, participation will be over and the study drug will no longer be administered.

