|  Children |  Healthy |  Fetal material, placenta, or dead fetus |
|  Non-English Speaking |  Prisoners |  Economically disadvantaged persons |
|  Decisionally Impaired |  Employees |  Pregnant women and/or fetuses |
|  Yale Students |  Females of childbearing potential | |

If patients are not competent to sign the informed consent, we will contact the healthcare proxy to provide informed consent for enrollment.

NOTE: Is this research proposal designed to enroll children who are wards of the state as potential subjects? Yes No (If yes, see Instructions section VII #4 for further requirements)

7. **Inclusion/Exclusion Criteria:** What are the criteria used to determine subject inclusion or exclusion?

Inclusion Criteria

- Age \geq 65
- Inpatient admission to general internal medicine service

Exclusion Criteria

- Expected lifespan or length of stay \leq 48 hours
- Non-English speaking
- Already taking melatonin at the time of randomization (at least one dose taken in the prior week)
- Already taking ramelteon (Rozerem) at the time of randomization (at least one dose taken in the prior week)
- Presence of delirium at the time of randomization
- Unable to take oral medications
- Subject or proxy unable to provide informed consent
- Unable to give consent within 18 hours of invitation or within 24 hours of being admitted to the medical floor
- Known allergy to melatonin
- Patients taking warfarin, nifedipine and fluvoxamine
- Patients with severe liver impairment (admission diagnosis of active liver disease such as cirrhosis or acute hepatitis)
- Unable to recall at least 2 of 3 words after distraction by asking the subject to name the days of the week backwards starting with Sunday.

8. How will **eligibility** be determined, and by whom?

A member of the research team will use the hospital EMR to screen admissions to the four participating general Internal Medicine floors for eligibility, based on the above inclusion and exclusion criteria. This will be accomplished via the OnCore and YCCI EPIC Support Services. The consent process will include a brief description of the study with an

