The principal investigator is responsible for monitoring the data, assuring protocol compliance, and conducting the safety reviews at the specified frequency on a monthly basis. During the review process the principal investigator will evaluate whether the study should continue unchanged, require modification/amendment, or close to enrollment.

The principal investigator or the Institutional Review Board (IRB) have the authority to stop or suspend the study or require modifications.

This protocol presents minimal risks to the subjects and adverse events or other problems are not anticipated. In the unlikely event that such events occur, Reportable Adverse Events (which are events that are serious or life-threatening and unanticipated (or anticipated but occurring with a greater frequency than expected) and possibly, probably, or definitely related) or unanticipated problems involving risks to subjects or others will be reported in writing within 48 hours to

the IRB (using the appropriate forms from the website) and any appropriate funding and regulatory agencies. The investigator will apprise fellow investigators and study personnel of all adverse events that occur during the conduct of this research project through regular study meetings.

- d. For multi-site studies for which the Yale PI serves as the lead investigator:
- i. How will adverse events and unanticipated problems involving risks to subjects or others be reported, reviewed and managed?
 - ii. What provisions are in place for management of interim results?
 - iii. What will the multi-site process be for protocol modifications?

12. **Statistical Considerations:** Describe the statistical analyses that support the study design.
13.

Primary Outcome:

Incidence of delirium per admission of medical geriatric patients

Incidence of delirium per patient days of hospitalization in medical admission of geriatric patients

Secondary outcomes:

Risk factors associated with incident delirium

Duration of delirium by study group

Hospital length of stay

Sample size based was estimated using openepi.com (similar results with Stata version 14 sample size calculator) based on control group incidence of delirium in medical subgroup of 30%. (Chen et al: Exogenous melatonin for delirium prevention: a meta-analysis of randomized controlled trials - Molecular Neurobiology online publication 21 July 2015) with relative risk reduction of 30 %.

Sample Size: X-Sectional, Cohort, & Randomized Clinical Trials

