Two-sided significance level(1-alpha):	95
Power(1-beta, % chance of detecting):	80
Ratio of sample size, Unexposed/Exposed:	1
Percent of Unexposed with Outcome:	30
Percent of Exposed with Outcome:	21
Risk/Prevalence Ratio:	0.7
Risk/Prevalence difference:	-9

Sample size estimation by the Fleiss method yielded a total sample size of 734 with 367 in each group.

Descriptive statistics such as percentages for binary categorical variables, means and standard deviations for continuous variables. Fisher's exact test or chi-square test will be used to compare categorical variables. For continuous variables we will use t-test of unequal variances for means for normally distributed variables and the Wilcoxon-Mann-Whitney where normal distribution cannot be assumed. Risk ratio will be calculated using Stata statistical program version 14. (StataCorp LP, [name]) Associations with covariates will be tested using logistic regression with presence of incident delirium as the dependent variable.

Person days to delirium will be compared between the two groups using Survival analysis with Kaplan Meier curves, logrank test and Cox proportional hazards (covariates include age, comorbidities, medication numbers, presence of risk factors for delirium – polypharmacy, use of psychotropic or sedating medications, and use of bladder catheters).

Upon completing enrollment and analysis of 367 subjects, [name], a independent statistical expert, will analyze the data. In addition, an independent geriatrician expert in delirium will review any equivocal CAM results and make a decision as to the occurrence of delirium.

SECTION VI: RESEARCH INVOLVING DRUGS, BIOLOGICS, RADIOTRACERS, PLACEBOS AND DEVICES

If this section (or one of its parts, A or B) is not applicable, state N/A and delete the rest of the section.

A. DRUGS, BIOLOGICS and RADIOTRACERS

1. **Identification of Drug, Biologic or Radiotracer:** What is (are) the **name(s)** of the drug(s) biologic(s) or radiotracer(s) being used? Identify whether FDA approval has been granted and for what indication(s).

Melatonin—FDA categorized as a dietary supplement for sleep aid

All protocols which utilize a drug, biologic or radiotracer **not** approved by, but regulated by, the FDA, or a radiotracer regulated by the RDRC, must provide the following information:

a. What is the Investigational New Drug (IND) **number** assigned by the FDA?

FDA IND 129224-Melatonin

b. Who holds the IND?

[name]

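### Duration of delirium is compared by arm with no analysis set or zero-day rule; tested among delirious subjects only, it is not a randomised comparison and can mislead in either direction

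*Combined protocol and SAP*

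**What the plan says.** Section V.12 (Statistical Considerations) gives three secondary outcomes. One is "Duration of delirium by study group", with nothing further: no start or end of an episode, no analysis set, no value for subjects without delirium, and no rule for death or discharge while delirious.

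The only stated method that reaches it is the general one in the same section: "For continuous variables we will use t-test of unequal variances for means for normally distributed variables", with Wilcoxon-Mann-Whitney where normality cannot be assumed.

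Three other statements bear on it:

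- Section V.7 excludes "Presence of delirium at the time of randomization", so every episode begins after randomisation.
- Section V.12 assumes "control group incidence of delirium in medical subgroup of 30"% "with relative risk reduction of 30"%, which gives 21% on melatonin. The arms are therefore planned to differ in how many subjects have a duration at all.
- Section V.3 (Research Plan) says that once delirium occurs "participation will be over and the study drug will no longer be administered". Section VII.9 ties the team's twice-daily evaluation to the time a subject remains in the study. Section VIII lists the daily CAM result among the data collected, but does not say whether collection continues after participation ends.

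**The concern.** A duration exists only for a subject who has become delirious. Becoming delirious is the primary outcome, and it is what melatonin is meant to change. The delirious subjects on melatonin are those whose delirium was not prevented; the delirious subjects on placebo include people whom melatonin would have kept free of it. These groups need not be alike, even though the full arms are.

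If melatonin mainly prevents short episodes, the cases left on melatonin are longer on average and the drug appears to prolong delirium. If it mainly prevents long ones, the remaining cases are shorter and it appears to shorten delirium. Neither requires that anyone's episode changed length. At stake is one of three secondary outcomes: a p-value between arms could be read as harm, or as a benefit on duration, when it reflects only which episodes were prevented.

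**Working it through.** **Plan's own figure.** Inputs from Section V.12: 30% and 21%, two-sided alpha 0.05, 80% power, equal arms. Pooled rate = 0.255.

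n per arm = [1.96·√(2·0.255·0.745) + 0.8416·√(0.30·0.70 + 0.21·0.79)]² / 0.09² = (1.2081 + 0.5160)² / 0.0081 = 367.

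This matches the stated 367 per arm, 734 in total.

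**Who has a duration.** Placebo: 367 × 0.30 = 110.1. Melatonin: 367 × 0.21 = 77.1. A cases-only test uses about 187 of 734 subjects, with about 33 fewer on melatonin because of the assumed effect.

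**Worked example (assumed lengths).** Suppose half the 110 placebo episodes last 1 day and half 5 days, and melatonin prevents 33 episodes without altering any other.

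- Placebo cases: (55·1 + 55·5)/110 = 3.00 days. Over all 367: 330/367 = 0.90.
- The 33 prevented are all short: (22·1 + 55·5)/77 = 3.86 days among cases. Over all 367: 297/367 = 0.81.
- The 33 prevented are all long: (55·1 + 22·5)/77 = 2.14 days among cases. Over all 367: 165/367 = 0.45.

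The cases-only means point in opposite directions. The all-subject means favour melatonin both times.

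**Range of selection.** The documents give no distribution of episode length, so I assume exponential lengths with mean 3 days. In every scenario melatonin prevents 30% of episodes overall and changes none. Let q be an episode's rank in length, from 0 (shortest) to 1 (longest), so that the mean of length × q is 2.25. If the chance of prevention is a − b·q, the mean among remaining cases is [3(1 − a) + 2.25b]/0.70. For a = 0.5, b = 0.4 this is (1.5 + 0.9)/0.70 = 3.43. For selection at the median, the lower half averages 3(1 − ln 2) = 0.92 and the upper half 3(1 + ln 2) = 5.08. Preventing 60% of the lower half only gives (0.2·0.92 + 0.5·5.08)/0.70 = 3.89. The all-subject mean is 0.30 × 3 = 0.90 on placebo, and 0.21 × the case mean on melatonin.

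| Prevention, by episode length | Mean, melatonin cases | Difference from 3.00 | Wilcoxon p<0.05 among cases | All-subject mean (difference from 0.90) |
|---|---|---|---|---|
| 30% at every length | 3.00 | 0.00 | 4–5% | 0.63 (−0.27) |
| 40% shortest to 20% longest | 3.21 | +0.21 | 8–9% | 0.675 (−0.225) |
| 50% shortest to 10% longest | 3.43 | +0.43 | 19–21% | 0.72 (−0.18) |
| 60% below median, none above | 3.89 | +0.89 | about 70% | 0.817 (−0.083) |
| 20% shortest to 40% longest | 2.79 | −0.21 | about 8% | 0.585 (−0.315) |
| 10% shortest to 50% longest | 2.57 | −0.43 | 19–20% | 0.54 (−0.36) |
| none below median, 60% above | 2.11 | −0.89 | about 70% | 0.443 (−0.457) |

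Rejection rates come from at least 2,000 simulated trials per scenario at 367 per arm. The unequal-variance t-test among cases is also affected: about 14% in the third row and 50% in the fourth.

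**What the all-subject measure can show.** In rows one, three and four, a Wilcoxon test on all-subject delirium days rejects in about 63% to 79% of trials. A chi-square test of incidence rejects in about 78% to 82%. About 70% to 79% of the values are zero, so the Wilcoxon test largely repeats the incidence comparison. A t-test on mean days in the same rows rejects in about 45–47%, 21% and 8–9%.

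**The case against.** **The plan does not say cases only.** This is right: the documents are silent on the analysis set. The cases-only reading rests on the ordinary meaning of duration and the absence of a zero rule. A reader might infer that the plan prescribes the biased comparison; it leaves it open. Only a descriptive table may have been intended, in which case saying so settles most of the point.

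**The bias has no known sign.** This also stands. A reader might infer that the trial is set up to show melatonin prolonging delirium. Nothing in the documents says which episodes melatonin would prevent, so false shortening is as possible as false prolongation. Under a mild gradient the effect is small, and without selection by length it is nil. The 70% figure needs every episode on one side of the median to be unpreventable.

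**Established delirium.** A reader might also infer that the outcome is offered as a test of melatonin as treatment. The stated purpose is prevention only. Nor do the documents support a contrast with the cited hip-surgery trial: the background table says treatment ran 5 days, but not whether dosing continued after onset.

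**The larger gap is follow-up.** With participation over at onset, the plan secures no study data from which to measure any duration. That affects every version of this outcome, including the remedy, so it has to be resolved too. It does not remove the selection problem, which remains once the data exist.

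**Conclusion.** The point holds in a limited form. The outcome is undefined and, read ordinarily, would test about 110 against 77 subjects selected by the primary outcome. That is not a randomised comparison. If prevention is related to episode length, the spurious difference is roughly 0.2 to 0.9 days in either direction, significant in about 8% to 70% of trials; otherwise it is zero.

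These sizes rest on an assumed mean episode of 3 days, exponential lengths, complete CAM data after onset, the planned 30% and 21%, and a drug that prevents episodes without altering their length. With no effect on incidence and none on who becomes delirious, the selection disappears. The primary incidence comparison and the sample size are unaffected. It should be settled before analysis because the wrong conclusion could go either way.

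**What to change.** - **Define the by-arm outcome in all randomised subjects:** days with delirium from randomisation to discharge or hospital day 15, whichever comes first, scored 0 if never delirious. Make the difference in mean days with its confidence interval the main estimate. If a Wilcoxon test is added, state that it largely repeats the incidence comparison and is not separate evidence on duration.
- **State how death and discharge while delirious are counted.**
- **Report duration among delirious subjects descriptively by arm,** with no between-arm test.
- **Reconcile Section V.3 with Section V.12,** so that routine CAM results after onset are collected; either version of the outcome needs them. Section V.3 describes routine CAM as once daily except on Verdi 4 West, where it is twice daily, so define what makes a day delirious. This concerns data collection only, not when study drug stops.

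**Cost:** rewording one secondary outcome, plus a change to the end-of-participation text and to data collection. The new measure mixes incidence with duration and has low power for duration itself; the descriptive table shows the two parts separately. Sample size and primary analysis do not change.

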explanation that the subject may receive no direct benefit from participating but patient care may in general improve if the study drug successfully prevents delirium. If the patient is interested in enrolling then the patient is asked to remember 3 words (apple, penny, and table) and then is distracted by being asked to recite the days of the week backwards starting with Sunday. If the subject can remember at least 2 of the 3 words then the entire consent is reviewed in depth and the subject is asked if he understands and if he has any questions before signing. A “teach back” will be accomplished to insure that the subject or the surrogate understands all the research aspects of the study. A Short CAM will then be performed by the investigator to evaluate for delirium. If delirium is not diagnosed via the Short CAM, the consent form will be completed and the patient entered into the trial.

9. **Risks:** Describe the reasonably foreseeable risks, including risks to subject privacy, discomforts, or inconveniences associated with subjects participating in the research.

Minimal risks are anticipated with this study however participation in the study may involve risks that are currently not known. Possible risks include the swallowing of an extra pill and the lack of ability to take melatonin for impaired sleep. While Micromedex lists side effects of melatonin, such as tachyarrhythmia, red/flushed skin, hypothermia, decreased glucose tolerance, abdominal cramps/diarrhea, confusion, decreased reaction time, sedation, sleep pattern disturbance, and worsening of depression, these are considered rare and usually with little clinical effect. A recent review in the journal *Clinical Drug Investigations* (Andersen LP, Gögenur I, Rosenberg J, Reiter RJ. *Clin Drug Investig.* 2016 Mar;36(3):169-75. doi: 10.1007/s40261-015-0368-5. PMID:26692007) concluded that the short-term use of melatonin is safe, even in extreme doses and that only mild adverse effects have been reported and are probably no different than placebo²⁹, with the possible exception of sleepiness. Other potential adverse effects include dizziness, headache, and nausea as described below, in section VI.2. Melatonin should have no major drug interactions or effects on other possible drug interventions in our subjects. Mild to moderate interactions with warfarin, nifedipine and fluvoxamine are noted in Micromedex and patients treated with these medications will not be included in the study.

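### The per-admission delirium comparison that sizes the trial has no planned baseline adjustment; prespecifying one would bring a modest gain in power

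*Combined protocol and SAP*

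**What the plan says.** Section V.12 (Statistical Considerations) names two primary outcomes: delirium per admission and delirium per patient-days. The sample size concerns the first. It assumes 30% delirium in controls, "with relative risk reduction of 30" per cent, and hence 21% on melatonin, which gives 734 subjects, 367 per arm. Section VII.1 sets the enrolment target at the same 734.

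For categorical variables the section names Fisher's exact or chi-square, and then says "Risk ratio will be calculated using Stata statistical program version 14". No covariate is attached to either. The next sentence is "Associations with covariates will be tested using logistic regression with presence of incident delirium as the dependent variable". Arm is not named in that model, which fits the secondary outcome on risk factors for delirium.

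Person-days to delirium are compared between arms by Kaplan-Meier, logrank and a Cox model. Its covariates include age, comorbidities, number of medications, psychotropic or sedating drugs and bladder catheters.

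Three items are fixed, or can be, before randomisation:
- **Age** is in the Section VIII data list.
- **Floor** is one of the four units in Section V.3.
- **Three-word recall** is tested during consent (Section V.8). A score below 2 of 3 is an exclusion (Section V.7).

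Randomisation is 1:1 in permuted blocks of 4, and no stratification factor is named (Section V.3).

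**The concern.** In a trial with a binary outcome, adjusting for prognostic variables measured before randomisation narrows the interval around the arm effect and removes the influence of chance imbalance on them. Here nothing in the allocation balances age or cognition, and the enrolment target equals the formula size with no allowance for withdrawals. The plan already adjusts for age in the Cox model for the other primary outcome, yet names no adjustment for the comparison that determined the sample size. What is at stake is some power, not validity.

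**Working it through.** **Inputs from Section V.12:** control risk 0.30, melatonin risk 0.21, difference 0.09, two-sided 5% level, 80% power, 1:1 allocation.

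**1. Reproduce the plan's figure.** Without continuity correction,

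n per arm = [z₀.₉₇₅ √(2 p̄ q̄) + z₀.₈₀ √(p₁q₁ + p₂q₂)]² / d²

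With p̄ = 0.255, 2 p̄ q̄ = 0.37995 (root 0.6164), and p₁q₁ + p₂q₂ = 0.2100 + 0.1659 = 0.3759 (root 0.6131). So n = [1.960 × 0.6164 + 0.8416 × 0.6131]² / 0.0081 = 1.7241² / 0.0081 = 367 per arm, 734 in total. Power at 367 is 80.0%. The planned size is exactly that of an unadjusted comparison.

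**2. Effect of adjustment.** If entry covariates explain a share R² of outcome variance, the effective size per arm is about 367 / (1 − R²). The documents give no R², so the range below is assumed. Worked case, R² = 0.05: effective n = 386.3; z = (0.09 × √386.3 − 1.2081) / 0.6131 = 0.915; power = 82.0%.

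| Assumed R² | Power at 367 per arm | n per arm for 80% power |
|---|---|---|
| 0 | 80.0% | 367 |
| 0.01 | 80.4% | 364 |
| 0.02 | 80.8% | 360 |
| 0.05 | 82.0% | 349 |
| 0.10 | 84.0% | 331 |
| 0.15 | 86.0% | 312 |

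**3. Check by simulation.** There were 4,000 trials per scenario with 367 per arm. A logistic model with arm, age, two-level recall (30% assumed to score 2) and four floors was standardised to a risk difference.

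| R² in controls | Crude power | Adjusted power |
|---|---|---|
| 0.014 | 80.1% | 81.3% |
| 0.053 | 79.8% | 81.9% |
| 0.140 | 80.2% | 85.4% |

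Adjusted type I error was 4.7% to 5.3%. In the weakest scenario the gain slightly exceeds the formula's. Part of that comes from the adjusted test's unpooled standard error: with no covariates at all, an unpooled test has power Φ[(1.7241 − 1.960 × 0.6131) / 0.6131] = 80.3%. In a separate run of 3,000 trials with a covariate unrelated to delirium, power was 79.5% adjusted and 79.7% crude, so a useless covariate costs almost nothing.

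**4. What recall alone could contribute.** Eligible subjects score only 2 or 3. If a share q scores 2, and their risk is RR times that of those scoring 3, then R² = q(1 − q)(p₁ − p₀)² / (0.255 × 0.745), with p₀ = 0.255 / (1 − q + q·RR) and p₁ = RR·p₀. For q = 0.3 and RR = 2: p₀ = 0.196, p₁ = 0.392, R² = 0.21 × 0.0385 / 0.190 = 0.04. Over q = 0.2 to 0.4 (assumed), R² is about 1% at RR 1.5, 4% at RR 2 and 10-11% at RR 3.

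**The case against.** The crude test is valid and is the analysis for which the trial was sized. That stands: nothing in the plan is wrong on this point. The gain is also likely to sit low in the range. Assume 30% score 2 on recall and floor has no effect. An age odds ratio of 1.2-1.3 per SD with a recall odds ratio of 1.5 gives R² of 1-2% and power of about 81%. Age 1.5 with recall 3 gives about 83%. That stands too.

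A reader might infer from the documents that floor is a strong predictor left out. Section V.3 does say that one unit differs in usual care ("with the exception of Verdi 4 West where the CAM is administered twice a day for all patients"), and Section V.10 gives background melatonin use of 7.2% and 12.3% on two floors. But every trial subject is assessed twice daily. Melatonin use in the prior week is an exclusion, and enrolled subjects are not to be prescribed it for sleep. Neither figure shows that delirium risk varies by floor.

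A reader might also infer that recall and floor will go unrecorded because Section VIII omits them. That list answers a question about protected health information and is not a case report form; it omits treatment arm as well. All that can be said is that the documents do not confirm that either will be recorded.

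None of this makes prespecified adjustment unsound. It limits how much can be claimed for it.

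**Conclusion.** The point holds as a modest efficiency gain over a valid crude analysis. The gain is about 0.4 to 2 points of power if the entry covariates explain 1-5% of outcome variance, about 4 points at 10% and about 6 points at 15%. These shares are assumptions, since the documents give no prognostic strength for age, recall or floor.

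Three stronger conclusions are tempting and not supported:
- **The primary analysis as a whole is unadjusted.** This is true of only one of the two primary outcomes.
- **Strong predictors known for every subject are being ignored.** Strength is not documented, and eligibility truncates recall to two values. Section VII.9 also expects some subjects to need surrogate consent because of cognitive deficits, without saying how they fit the recall exclusion.
- **The arm effect will be reported as an odds ratio.** At the design rates this would be (0.21/0.79) / (0.30/0.70) = 0.62 against a risk ratio of 0.70. But the plan names the risk ratio and does not put arm in the logistic model.

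**What to change.** Before any unblinded look, including the independent statistician's analysis that Section V.12 places at 367 subjects, add to that section:

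- **Primary per-admission analysis:** logistic regression with arm and age, plus the entry recall result (2 vs 3 words) if it is recorded. Floor is optional.
- **Reported effect:** standardised (marginal) risk ratio and risk difference with 95% CI. These average each subject's predicted risk under each arm, so the estimate stays on the planned risk-ratio scale.
- **Supporting results:** the crude chi-square and crude risk ratio.
- **Covariate rule:** only variables measured before randomisation. The Cox list should not be carried over as it stands, because bladder catheters and sedating drugs are not restricted to entry and may arise after randomisation.

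The cost is a paragraph of analysis text fixed in advance and one item recorded at entry. The surrogate-consent route in Section VII.9 must also be reconciled with the recall exclusion in Section V.7, so that it is clear which recall values can occur. No additional subjects are needed, and the sample size can stay at 734.
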